**4.2.2.2      Restrictions on diet and life style**

Not applicable

**4.2.2.3      Restrictions regarding women of childbearing potential**

Women of childbearing potential must use the contraception methods described in the patient information.

**4.3            TREATMENT COMPLIANCE**

The investigator will maintain accurate records of receipt of all study medication, including the date, exact time point of receipt. In addition, accurate records will be kept regarding the total dosage administered to each individual patient in the study.

Actual weighing of the patient is preferred when it can be performed without inducing delays. The treatment effect is time-dependent; therefore treatment must be started as early as possible within 4.5 hours after onset of stroke symptoms.

## **5. VARIABLES AND THEIR ASSESSMENT**

### **5.1 TRIAL ENDPOINTS**

#### **5.1.1 Endpoints of efficacy**

##### **5.1.1.1 Primary Efficacy Endpoint**

The primary efficacy endpoint is the percentage of patients with mRS 0-1 (favourable outcome) at visit 5 (i.e., day 90) after stroke onset by face-to-face interview with patient.

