## **5.2 ASSESSMENT OF EFFICACY**

The primary study endpoint is functional independence as measured by the mRS (score of 0-1) assessed at 90 days after stroke onset by face-to-face interview with patient.

Functional outcome (day 90) is defined by mRS, excellent (mRS 0-1) vs. unfavourable outcome (mRS 2-6), which is the primary study endpoint.

The secondary efficacy endpoint will be global outcome analysis of four neurological and disability scores combined.

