### **Modified Rankin Scale:**

The mRS is a tool used to evaluate disability after a stroke and will be collected at day 30 and at day 90.

The grading of the score is as follows:

Grade 0: no symptoms at all

Grade 1: no significant disability despite symptoms;  
able to carry out all usual duties and activities

Grade 2: slight disability: unable to carry out all previous activities but able to look after own affairs without assistance

Grade 3\*: moderate disability: requiring some help but able to walk without assistance

Grade 4: moderate-severe disability: unable to walk without assistance and unable to attend to own bodily needs without assistance

Grade 5: severe disability: bedridden, incontinent, and requiring constant nursing care and attention.

Grade 6: Dead

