5.1 PRIMARY ENDPOINT(S)

The primary efficacy endpoint is the percentage of patients with mRS 0-1 (favourable outcome) at Visit 5 (i.e., Day 90) after stroke onset by face-to-face interview with patient. A patient is considered to be a mRS 0-1 responder (response value set to 1) if he/she obtained a response of 0 or 1 on the modified Rankin scale otherwise the response value will be set to 0.

The primary safety endpoint is the percentage of patients with symptomatic intracranial haemorrhage (sICH) centrally evaluated by DMC consultants according to ECASS III definition within the whole study period. ECASSIII definition is any apparently extravascular blood in the brain or within the cranium that was associated with clinical deterioration (defined by an increase in the National Institute of Health Stroke Scale (NIHSS) score of 4 or more points), or that led to death and that was identified as the predominant cause of the neurological deterioration.

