In case of NIHSS missing at baseline and at all post baseline time points, then the individual values for post baseline measurements will stay missing and the total NIHSS score for all post baseline data will be imputed depending on survival status (dead/missing/alive, alive will be handled the same as missing in this scenario).

Barthel index is present only at Visit 4 and Visit 5. In case of missing items for the Barthel index at Visit 4, the worst value will be imputed for these items.

Furthermore, in cases where one of more individual items is missing, the total score must be set to missing for the observed case type of analysis.

Table 6.6:1 Handling of missing data

Endpoint	Baseline value	Baseline imputation value	Post-baseline value at visit	Patient dead/alive at visit	Post baseline imputation value at visit
modified Rankin scale			Available	Alive	NA
			Missing	Alive	LOCF or worst excluding death (5) if missing at Visit 4
			Missing	Dead	Worst (6)
			Missing	Missing	Worst excluding death (5)
Barthel Index			Available	Alive	NA
			Missing	Alive	LOCF or worst if missing at Visit 4
			Missing	Dead	Worst (0)
			Missing	Missing	Worst (0)
Glasgow outcome			Available	Alive	NA
			Missing	Alive	Worst excluding death (4)
			Missing	Dead	Worst (5)
			Missing	Missing	Worst excluding death (4)
NIHSS total score	Available or missing	If missing impute best value (0)	Available	Alive	NA
	Available or missing	If missing impute best value (0)	Missing	Alive	LOCF or worst (42) if all post-baseline were missing
	Available or missing	If missing impute best value (0)	Missing	Dead	Worst (42)
	Available or missing	If missing impute best value (0)	Missing	Missing	Worst (42)

NIHSS Total score:

The total score of the NIHSS is the sum of the **15** individual item scores: level of consciousness (1), LOC questions (2), LOC commands (3), best gaze (4), visual (5), facial paresis (6), motor arm right (7), motor arm left (8), motor leg right (9), motor leg left (10), limb ataxia (11), sensory (12), best language (13), dysarthria (14), extension and inattention (15).

For the calculation of the total score:

The scores of '9' on motor (7-10) indicating amputation or joint fusion on motor arm right or left, motor leg right or left will be replaced by (4) for post baseline value and by best case (0) at baseline.

A score of '9' on dysarthria (14) will be replaced by the worst case value (2) for post baseline value and by best case (0) at baseline.

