This rule is to be applied for observed cases and WLOCF.

The censoring rules for time to death (survival time, [day]) at Day 90 and censoring flag will be calculated as following manner:

➤ **for a dead patient:**

death=yes

censoring flag=0

survival time=date of death – date of start bolus +1

if survival time >90 (patient alive at Visit5)

then death=no, censoring flag=1, survival time=90

➤ **for patient alive at Visit 5:**

death=no

censoring flag=1

survival time= date of last contact – date of start bolus +1

if survival time>90 then survival time=90

➤ **for a lost to follow up patient:**

death = no

censoring flag=1

if « last date patient known to be alive » is known

then survival time= last date patient known to be alive – date of start bolus +1

if « last date patient known to be alive » is unknown

then survival time= date of last contact – date of start bolus +1

if survival time>90 then survival time=90

Date of last contact is the maximum of {date of last measurement or visit, date of trial completion, last available date from AE and last available date from CM}.

The censoring rules for time to death (survival time, [day]) overall study and censoring flag will be calculated as following manner:

All deaths are taken into account whatever their time of occurrence, and even if they occurred after the 97 days (90 days +7).

➤ **for a dead patient:**

death=yes
censoring flag=0
survival time=date of death – date of start bolus +1

➤ **for patient alive at Visit 5:**

death=no
censoring flag=1
survival time= date of last contact – date of start bolus +1

➤ **for a lost to follow up patient:**

death = no
censoring flag=1
if « last date patient known to be alive » is known
 then survival time= last date patient known to be alive – date of start bolus +1
if « last date patient known to be alive » is unknown
 then survival time= date of last contact – date of start bolus +1

Date of last contact is the maximum of {date of last measurement or visit, date of trial completion, last available date from AE and last available date from CM}.

The length of stay in hospital will be calculated as follows:

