6.7 BASELINE, TIME WINDOWS AND CALCULATED VISITS

The table below presents the visit structure according to the study flowchart depending on the time window scheduled in the CTP.

Table 6.7: 1 Visit structure

Period	Baseline	Trial drug admin.	On-treatment & Post-treatment					
Visit number per protocol	V1A		V1B#	V1C#	V2	V3	V4	V5
Planned study window	-4.5-0 hour	↔x→ 60 mins	1 hour ± 15 mins	2 hrs ± 30 mins	24 hrs ± 2hr	7 days ± 3 day	30 days ± 3 days	90 days ± 7 days
Study Day	← D0 →			D1	D7	D30	D90	
Visit description*	Baseline		Day0 (1H)	Day0 (2 H)	Day1	Day7	Day30	Day90

*label to be used in tables.

‘Baseline’ is defined as from enrolled in this study to the start time of bolus treatment administration

‘Study Day’ is calculated from the date & time of starting bolus treatment administration.

date & time is calculated from the date & time of starting infusion treatment administration.

Start of treatment:

The start of treatment (used for survival start time, length of stay in hospital, treatment at onset for adverse event) will be the **start of bolus treatment administration**; end of treatment is the end of infusion/drug/treatment administration.

Baseline value:

The baseline value will be the value recorded at V1A (last available value before the start of bolus treatment).

Change from baseline:

The change from baseline for any efficacy or safety endpoints (Vital signs) will be calculated as: value after baseline – value at baseline (V1A).

All efficacy analyses will be based on ‘nominal visits’ (CRF raw data visit) which will be labelled as indicated in the ‘Visit description’ row in tables, listings and graphs.

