7.4 PRIMARY ENDPOINT(S)

Primary analysis

The primary efficacy endpoint is the percentage of mRS 0-1 (favourable outcome) responder at Visit 5 after stroke onset by face-to-face interview with patient. The proportion of patients with mRS 0-1 will be presented with corresponding 95% confidence intervals (CIs). The imputation rules described in [Section 6.6](#) will be applied for the primary analysis. The observed case analysis, that is the proportion of patients with mRS 0-1 observed at Visit 5, will be performed as sensitivity analysis.

The null hypothesis of $p \leq 40\%$ versus the alternative hypothesis of $p > 40\%$ will be tested using a one sample t-test at two-sided significance level of 0.05. The horizontal stacked bar graphs of each level in the ordinal mRS will be presented.

The primary safety endpoint is the proportion of patients with symptomatic intracranial haemorrhage (sICH) evaluated by DMC consultants within whole study period. The proportion of patients with sICH will also be presented along with corresponding 95% CIs.

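### The primary endpoint is defined only by face-to-face interview with the patient, and neither document says whether a Day 90 mRS obtained by telephone or from a caregiver counts

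*Protocol*

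**What the plan says.** The mode of assessment is part of the endpoint wherever the endpoint is stated. Protocol 5.1.1.1 has mRS 0-1 "at visit 5 (i.e., day 90) after stroke onset by face-to-face interview with patient". Protocol 5.2 has it "assessed at 90 days after stroke onset by face-to-face interview with patient". Protocol 7.3.1 and SAP 5.1 carry the same condition, and SAP 7.4 speaks of a "responder at Visit 5 after stroke onset by face-to-face interview with patient". No other mode or informant is named in the available text. The table part of the protocol flow chart is largely missing from that text; its surviving footnotes offer no alternative.

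The mRS "will be collected at day 30 and at day 90" and at no other time (Protocol 5.2). Visit 4 may fall on Days 27 to 33 and Visit 5 on Days 83 to 97 (Protocol 6.3.1).

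Protocol 7.5 accepts that functional outcomes of survivors may be missing. For a living patient with no Day 90 mRS, SAP Table 6.6:1 prescribes "LOCF or worst excluding death (5) if missing at Visit 4". If vital status is unknown the score is 5, and if the patient has died it is 6.

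The responder derivation in SAP 5.1 depends on the score: a patient responds "if he/she obtained a response of 0 or 1 on the modified Rankin scale otherwise the response value will be set to 0". SAP 6.7 bases efficacy analyses on the nominal visit recorded in the CRF. Neither rule filters on how the score was obtained.

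**The concern.** Some living patients will be unable to come to the clinic at Day 90. The plan anticipates missing scores in survivors but does not tell the site what to do if the patient or a caregiver can be reached by other means. Read literally, the endpoint leads a site to leave the field empty, and an obtainable Day 90 outcome is then replaced by an older one.

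Three things are at stake.

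- **Misclassification in both directions.** A patient with mRS 1 at Day 30 who is disabled at Day 90 is counted as a success. A patient with mRS 2 at Day 30 who has recovered by Day 90 is counted as a failure. Patients who cannot attend are unlikely to be a random subset, so the errors need not cancel in a single-arm rate tested against 40%.
- **Inconsistent handling.** With about 15 sites, one may enter a telephone score and another leave it blank for an identical patient. Nothing in the documents provided would show which was done.
- **No recovery later.** The observed-case sensitivity analysis in SAP 7.4 cannot bring back scores that were never recorded.

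**Working it through.** **Inputs from the documents.** n = 120; null rate 40%; two-sided alpha 0.05; assumed rate 55%; stated power 91.5% (Protocol 7.2 and 7.7). Drop-outs are not replaced (Protocol 6.3.2), and the sample size section mentions no allowance for missing outcomes.

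**The plan's own figure.** Normal approximation with the null variance in the critical value:

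power = Φ[(p1 − p0 − 1.96·√(p0·q0/n)) / √(p1·q1/n)]

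= Φ[(0.55 − 0.40 − 1.96 × 0.04472) / 0.04541] = Φ(1.373) = 91.5%.

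The stated power reproduces, as do the other two rows of Table 7.7:1 (79.4% and 84.2%).

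**Responders needed.** z = (x/120 − 0.40)/0.04472 gives 1.86 for x = 58 and 2.05 for x = 59, so 59 of 120 is the smallest passing count. The Wilson lower limit at 59 is 40.4%, which agrees. The binomial probability of 59 or more at 55% is 91.5%, so this rule matches the stated power and is used below. Each patient is worth 1/120 = 0.83 percentage points.

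**Age of the carried-forward score.** Only Day 30 precedes Day 90, so LOCF for the mRS can only mean Visit 4. The gap is nominally 90 − 30 = 60 days. The visit windows allow 83 − 33 = 50 to 97 − 27 = 70 days.

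**Illustration on assumed rates.** Let m be the proportion alive but not seen in person at Day 90, all with a Visit 4 score. Let d be the amount by which their Day 30 response rate lies below their Day 90 rate. Both are assumptions, because the documents give neither. With a true Day 90 rate of 55% in everyone, the analysed rate is (1 − m) × 0.55 + m × (0.55 − d) = 0.55 − m·d, and the expected loss is 120·m·d responders.

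| m | d | Analysed rate | Responders lost | Power (59 or more) |
|---|---|---|---|---|
| 0 | – | 55.00% | 0 | 91.5% |
| 5% | 5 points | 54.75% | 0.3 | 90.6% |
| 10% | 10 points | 54.00% | 1.2 | 87.6% |
| 15% | 15 points | 52.75% | 2.7 | 81.0% |

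Taking 91.5% as the comparison assumes that remote contact would recover every missing score correctly, so the differences are upper bounds on what the fix regains under these assumptions. The table covers only the case where Day 30 is worse than Day 90. If Day 30 responders among the non-attenders have worsened, d is negative and the analysed rate is inflated against the 40% threshold.

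**The case against.** The strongest reply is that no score is actually excluded. A reader might infer from the endpoint wording that a telephone or caregiver score is inadmissible. The documents do not support that: nothing tells sites to withhold such a score or the analyst to blank it, and under SAP 5.1 and 6.7 a value entered at Visit 5 would be analysed. What stands is a silence that sites can resolve differently.

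A reader might also infer from the SAP censoring rules, with their branch "if « last date patient known to be alive » is known", that sites will be in touch at Day 90 and could ask for the mRS in the same call. That line only sets the survival time of patients lost to follow-up. The date may fall well before Day 90, and the rule does not show that any Day 90 call takes place.

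A third tempting step is to quote the effect of assigning mRS 5. If every non-attender were set to failure, power would be 77.9% at 5% (rate 52.25%) and 56.5% at 10% (rate 49.5%). But a patient who has been reached is known to be alive and receives the Visit 4 score. Those figures need both visits to have been missed and do not describe the ordinary case.

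In-person scoring is also a defensible default in an open-label trial, because a uniform mode limits assessor variation. Inability to converse, as in aphasia, need not prevent grading at an in-person visit. The protocol asks for 90-day follow-up and an end-of-trial evaluation where possible (6.2.3, 6.3.2), which should keep non-attendance down. These points limit the size of the problem, but none says what happens when attendance fails. Finally, the CRF and the full flow chart could not be seen, so an instruction there cannot be ruled out.

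**Conclusion.** The point holds as a gap in the ascertainment rule: one mode is named, no fallback is given, and the status of any other Day 90 score is left open. For a living patient who cannot attend, the likely result of following the wording is a Visit 4 score about 60 days old, with mRS 5 only when Visit 4 is missing too.

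The effect is modest at low non-attendance and becomes material only towards the top of the assumed range: under one point of power at 5% and 5 points, about four points at 10% and 10 points, and about ten at 15% and 15 points. In that direction the bias works against the drug. The opposite direction, where earlier responders have deteriorated, is possible and is not quantified because the documents give nothing on change between Day 30 and Day 90. This is a worthwhile, inexpensive improvement rather than a flaw that invalidates the primary analysis.

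**What to change.** In Protocol 5.1.1.1, 5.2 and 7.3.1 and in SAP 5.1 and 7.4:

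- Keep the face-to-face interview as the default.
- Where it is not possible within Day 83 to 97, accept a structured telephone interview with the patient or, if the patient cannot answer, with the caregiver.
- Record the mode and informant in the CRF.
- Use this score before any imputation under SAP 6.6.
- Repeat the primary analysis with telephone and caregiver scores treated as missing under the existing SAP 6.6 rules, so that the result on in-person scores remains visible.

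If the sponsor prefers in-person scores only, the documents should say so and state that other scores are set to missing, so that all sites act alike.

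The cost is a short amendment, a CRF entry for mode and informant, and a call by existing site staff. Remote scoring is somewhat less reliable than in-person scoring, though it replaces only values that would otherwise be imputed. It does not supply the Day 90 NIHSS, so the global outcome for these patients would still need imputation.

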##### **5.1.1.2 Secondary Efficacy Endpoint**

The percentage of global outcome responder at visit 5 (i.e., day 90) if he/she obtains the following results at visit 5 (i.e., day 90) (for all of the 4 endpoints)

mRS score of 0 to 1

Barthel Index score  $\geq 95$

NIHSS score of 0 to 1

Glasgow Outcome Scale score of 1

### **5.1.2 Endpoints of safety**

#### **5.1.2.1 Primary Safety endpoints**

The percentage of patients with symptomatic intracranial haemorrhage (sICH) centrally evaluated by DMC consultants according to ECASS III definition within the whole study period.

#### **5.1.2.2 Secondary Safety Endpoints**

- Patient survival probability at visit 5 (censoring at day 90)
- Frequency of death related to stroke or of neurological causes
- Frequency and severity of adverse events
- Incidence of cerebral herniation and symptomatic edema

## **5.2 ASSESSMENT OF EFFICACY**

The primary study endpoint is functional independence as measured by the mRS (score of 0-1) assessed at 90 days after stroke onset by face-to-face interview with patient.

Functional outcome (day 90) is defined by mRS, excellent (mRS 0-1) vs. unfavourable outcome (mRS 2-6), which is the primary study endpoint.

The secondary efficacy endpoint will be global outcome analysis of four neurological and disability scores combined.

### **Modified Rankin Scale:**

The mRS is a tool used to evaluate disability after a stroke and will be collected at day 30 and at day 90.

The grading of the score is as follows:

Grade 0: no symptoms at all

Grade 1: no significant disability despite symptoms;  
able to carry out all usual duties and activities

Grade 2: slight disability: unable to carry out all previous activities but able to look after own affairs without assistance

Grade 3\*: moderate disability: requiring some help but able to walk without assistance

Grade 4: moderate-severe disability: unable to walk without assistance and unable to attend to own bodily needs without assistance

Grade 5: severe disability: bedridden, incontinent, and requiring constant nursing care and attention.

Grade 6: Dead

### **Barthel Index score**

It will be used to evaluate the recovery of neurological functions at day 30 and day 90.

### **Glasgow Outcome Scale score**

The Glasgow Outcome Score applies to patients with brain damage allowing the objective assessment of their recovery in five categories. This allows a prediction of the long-term course of rehabilitation to return to work and everyday life. It will be collected at day 90.

The Glasgow Outcome Scale is a 5-level score:

1. Good Recovery
2. Moderately Disabled
3. Severely Disabled
4. Vegetative State
5. Dead

### **National Institutes of Health Stroke Scale (NIHSS)**

The NIHSS will be recorded, if it had been collected at the time of qualifying (index) stroke. In patients, where NIHSS has not been done at the time of index stroke, it will be performed at study entry (at Visit 1). It is a tool used by healthcare providers to objectively quantify the impairment caused by a stroke. The NIHSS is composed of 11 items, and for each item a score of 0 typically indicates normal function in that specific ability, while a higher score is indicative of some level of impairment. The individual scores from each item are summed in order to calculate a patient's total NIHSS score. The maximum possible score is 42, with the minimum score being a 0. Clinical outcome will also be assessed by NIHSS scoring at 2 hours, 24 hours, and on day 7, 30 and 90.

## **5.3 ASSESSMENT OF SAFETY**

Patients are monitored in the stroke unit or Intensive Care Unit (ICU). For assessment of safety, incidence and severity of adverse events including mortality at day 90, stroke-related and neurological, including cerebral herniation rate and symptomatic oedema, deaths, and symptomatic cerebral bleeding will be evaluated. Intracranial haemorrhage will be assessed separately.

Safety monitoring is performed by an independent Data Monitoring Committee (DMC). The details will be described in the DMC Charter.

### **5.3.1 Assessment of symptomatic intracranial haemorrhage (sICH)**

According to this protocol, sICH (ECASS III criteria) is defined as: any apparently extravascular blood in the brain or within the cranium that was associated with clinical

deterioration (defined by an increase in the NIHSS score of 4 or more points), or that led to death and that was identified as the predominant cause of the neurological deterioration. sICH event will be firstly evaluated by investigator. The DMC consultants will evaluate all the patients with NIHSS score increase of at least 4 any time after treatment (including all the sICH events evaluated by investigator).

